10.4. Missing Data

Subjects with worsening of disease before Week 12 and subjects who meet the criteria for worsening disease after Week 12, as defined in Section 5.1.1, will be considered as having a treatment nonresponse outcome in the analysis of all binary efficacy endpoints, including the primary endpoint. In addition, subjects who initiate an agent not allowed in combination with the study treatment that can affect the efficacy of the study treatment, such as an immunosuppressant or corticosteroid, or who have an increase in dose over baseline levels for treatment of worsening disease symptoms will be considered nonresponders for binary responder-type endpoints thereafter or be handled by per protocol analysis.

Subjects discussed above will be considered as having a known outcome at the analysis timepoint (ie, a treatment failure outcome) and not as having missing data. Subjects who discontinue the double-blind treatment period for reasons other than worsening disease or adverse event related to UC will be considered as having missing data and will be handled in the primary and sensitivity analyses as follows.

A full description of the handling of missing data will be provided in the SAP.

Primary Method of Handling Missing Data

In the primary analysis of the primary endpoint and main analyses of all binary responder-type endpoints, all subjects with missing data, regardless of reason for missingness, will be considered as non-responders.

In the main analysis of continuous or score endpoints, such as changes from baseline in MMS subscores, biomarker measures, urgency NRS, and health-related quality of life measures, these continuous endpoints will be analyzed with a mixed-effect model with repeated measures. Detailed methods will be provided in the SAP.

Sensitivity Analyses for Missing Data

Sensitivity analyses will be performed under several alternative assumptions regarding missing data, ie, data missing intermittently, after discontinuation from the double-blind study for reasons other than worsening diseases, or after initiation of excluded medications.

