		(7) Efficacy analyses will be based on the estimand framework.	(7) Per protocol analysis set is irrelevant and is removed.
		(8) Per FDA comments.	(8) Endoscopic improvement at Week 12 and complete symptomatic remission at Week 12 and Week 52 are considered as key secondary endpoints and are included in type I error controlled family. Symptomatic remission at Week 52 is now considered as a secondary endpoint.
		(9) Add additional exploratory endpoints.	(9) Clinically meaningful improvement in bowel urgency at Week 12 and Week 52;

Table 2. Summary of Modification

Version/ Date	Associated Protocol Amendment	Rationale	Specific Modification
			bowel urgency remission at Week 12 and Week 52; complete bowel urgency remission at Week 12 and Week 52 are added as exploratory endpoints.
		(10) Add two secondary endpoints.	(10) 12-week corticosteroid-free clinical remission at Week 52 among participants receiving corticosteroids at baseline; 4-week corticosteroid-free clinical remission at Week 52.

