2.2.3. Primary Estimand (Estimand 1)

The primary estimand of this study is a composite estimand, which estimates the effect of randomized treatment accounting for treatment adherence and response.

- Treatment: Etrasimod 2 mg vs Placebo
- Population: Participants with mildly to moderately active UC as defined in 2022
 FDA Draft Guidance; Ulcerative Colitis: Developing Drugs for Treatment (Section 8 References)
- Variable: primary efficacy endpoint of clinical remission at week 52 and all binary efficacy endpoints as described in Sections 3.1, 3.2.1 and 3.4.1
- Intercurrent events: the following intercurrent events are defined:
 - 1) Discontinue the study treatment during the double blind treatment period for any reasons
 - 2) Initiate a rescue medication for UC (Section 9.3)
 - 3) Have an increase in dose over baseline levels in their existing UC medication following the rules in Section 9.3

4) Have a rescue non-drug treatment (eg, colectomy, ileostomy, or sigmoidectomy) during the study (Section 9.3)

Participants having any of the intercurrent events as defined in 1) - 4) above will be considered as nonresponders, that is, have a known outcome of nonresponse at applicable timepoints. Missing measurements due to other reasons will be treated as missing. The method of dealing with missing data is presented in Section 5.3

 Population-level summary: Proportion of participants who are responders in each treatment group and differences in proportions of responders between Etrasimod 2 mg group and placebo group.

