9.3. Classification of Rescue Therapy

This appendix outlines the algorithm for the Pfizer clinical team/medical reviewers to classify rescue therapies for ulcerative colitis (UC) in a blinded manner. This will help establish intercurrent events for the efficacy estimands. All rescue therapies identified by the medical reviewers per the algorithm below will be imported in programming. This process will be repeated until database lock and the list of all rescue therapies identified will be finalized before study unblinding.

Only medications and medical procedures reported on the electronic case report forms (eCRFs) can be assessed whether they are rescue therapy for UC. If the exposure happens in the follow-up period (beginning on or after the date of last study treatment administration), then it would not be considered as a rescue therapy. Impact of rescue therapy use in the analysis is timing-dependent, eg, if a participant starts a rescue therapy between their Week 12 and Week 52 endpoint assessments, then it may have potential impact on Week 52 endpoint analysis but will have no impact on Week 12 endpoints. The rules outlined below apply to both new use and increase in dose from Baseline.

Biologics with immunomodulatory properties

- Rule:
 - Any exposure after first dose
- List of medications:
 - AntiTNFα antibodies:
 - ADALIMUMAB
 - CERTOLIZUMAB
 - CERTOLIZUMAB PEGOL
 - GOLIMUMAB
 - INFLIXIMAB
 - Other Biologics:
 - USTEKINUMAB
 - VEDOLIZUMAB
 - MIRIKIZUMAB

Nonbiologics with immunomodulatory properties

- Immunosuppressants
 - Rules to consider for Week 12 efficacy endpoints:
 - After first dose and up to and including Week 8: any increase from baseline for more than 5 days
 - After Week 8: Any dose above baseline
 - Rules to consider for Week 52 efficacy endpoints:
 - After Week 12 and up to and including Week 40: any increase from baseline for more than 5 days
 - After Week 40: Any dose above baseline
 - List of medications:
 - Thiopurines
 - MERCAPTOPURINE
 - o AZATHIOPRINE
 - TIOGUANINE
 - METHOTREXATE
 - METHOTREXATE SODIUM
- 5-ASA COMPOUNDS
 - Rules to consider for Week 12 efficacy endpoints:
 - After first dose and up to and including Week 8: any increase from baseline for more than 5 days
 - After Week 8: Any dose above baseline
 - Rules to consider for Week 52 efficacy endpoints:
 - After Week 12 and up to and including Week 40: any increase from baseline for more than 5 days
 - After Week 40: Any dose above baseline

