- List of medications:
 - MESALAZINE
 - MESALAMINE
 - BALSALAZIDE
 - BALSALAZIDE DISODIUM DIHYDRATE
 - BALSALAZIDE SODIUM
 - OLSALAZINE SODIUM
 - SULFASALAZINE
 - BECLOMETASONE W/MESALAZINE
- Routes:
 - ORAL
 - RECTAL

Other small molecule immunomodulatory active agents

- Rules to consider for Week 12 efficacy endpoints:
 - After first dose and up to and including Week 8: any increase from baseline (including new use) for more than 5 days
 - After Week 8: Any dose above baseline
- Rules to consider for Week 52 efficacy endpoints:
 - After Week 12 and up to and including Week 40: any increase from baseline (including new use) for more than 5 days
 - After Week 40: Any dose above baseline
- List of medications:
 - CICLOSPORIN
 - TACROLIMUS
 - TOFACITINIB
 - TOFACITINIB CITRATE

- UPADACITINIB
- Systemic glucocorticoids
 - Systemic glucocorticoids given via oral or rectal routes of administration
 - Rules to consider for Week 12 efficacy endpoints:
 - After first dose and up to and including Week 8: any increase from baseline for more than 7 days
 - After Week 8: Any dose above baseline
 - Rules to consider for Week 52 efficacy endpoints:
 - After Week 12 and up to and including Week 40: any increase from baseline for more than 7 days
 - o After Week 40: Any dose above baseline
 - List of medications:
 - BETAMETHASONE
 - BETAMETHASONE DIPROPIONATE
 - BETAMETHASONE SODIUM PHOSPHATE
 - DEXAMETHASONE
 - DEXAMETHASONE SODIUM PHOSPHATE
 - DEXAMETHASONE VALERATE
 - METHYLPREDNISOLONE
 - METHYLPREDNISOLONE SODIUM SUCCINATE
 - o PREDNISOLONE
 - PREDNISOLONE SODIUM PHOSPHATE
 - PREDNISOLONE METASULFOBENZOATE SODIUM
 - o PREDNISONE
 - TRIAMCINOLONE
 - HYDROCORTISONE

- HYDROCORTISONE ACETATE
- HYDROCORTISONE BUTYRATE
- HYDROCORTISONE SODIUM SUCCINATE
- Routes:
 - o ORAL
 - o RECTAL
- Systemic given via parenteral routes of administration
 - Rule for Week 12 endpoint:
 - Any exposure after first dose up to Week 12
 - Rules for Week 52 endpoint:
 - After Week 12 and up to and including Week 40: more than one dose
 - Any exposure after Week 40
 - List of medications:
 - BETAMETHASONE
 - BETAMETHASONE DIPROPIONATE
 - BETAMETHASONE SODIUM PHOSPHATE
 - DEXAMETHASONE
 - DEXAMETHASONE SODIUM PHOSPHATE
 - DEXAMETHASONE VALERATE
 - METHYLPREDNISOLONE
 - METHYLPREDNISOLONE SODIUM SUCCINATE
 - PREDNISOLONE
 - PREDNISOLONE SODIUM PHOSPHATE
 - PREDNISOLONE METASULFOBENZOATE SODIUM
 - PREDNISONE

- TRIAMCINOLONE
- HYDROCORTISONE
- HYDROCORTISONE ACETATE
- HYDROCORTISONE BUTYRATE

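### SAP 9.3 opens the Week 52 rescue window only after Week 12 for all seven non-biologic drug groups, so early rescue that has ended, a nonresponse under protocol 10.4, can be scored as Week 52 remission

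*SAP*

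**What the plan says.** Protocol 10.4 deals with subjects who start a disallowed agent that can affect efficacy, or whose dose rises above baseline for worsening symptoms. They "will be considered nonresponders for binary responder-type endpoints thereafter or be handled by per protocol analysis". The same section assigns a nonresponse outcome on all binary endpoints, the primary included, to "Subjects with worsening of disease before Week 12 and subjects who meet the criteria for worsening disease after Week 12". Neither rule restarts at Week 12.

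The SAP's primary estimand (2.2.3) makes rescue medication, and dose increases in existing UC medication, intercurrent events as classified in Section 9.3. Participants with such an event "have a known outcome of nonresponse at applicable timepoints". SAP 5.3.1.1 uses nearly the same words. Neither section says which timepoints are applicable.

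SAP 9.3 gives separate Week 12 and Week 52 rules by drug group. For immunosuppressants and 5-ASA the Week 52 rule opens "After Week 12 and up to and including Week 40: any increase from baseline for more than 5 days". For ciclosporin, tacrolimus, tofacitinib and upadacitinib it reads "After Week 12 and up to and including Week 40: any increase from baseline (including new use) for more than 5 days". Oral or rectal systemic glucocorticoids, parenteral glucocorticoids, budesonide and beclomethasone follow the same pattern. Biologics and medical procedures count from first dose.

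On the protocol's alternative route, SAP 2.1 (Table 2, item 7) says: "Per protocol analysis set is irrelevant and is removed".

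**The concern.** The protocol's rule carries forward: once rescued, a subject remains a nonresponder. The SAP's rule for non-biologic drugs resets at Week 12. Following the SAP as written can turn a subject whom the protocol calls a nonresponder into a Week 52 remitter. The estimand is meant to reflect both adherence to randomized treatment and response, so the reset changes what the primary endpoint measures.

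The SAP is also uneven within one section. One early dose of a biologic counts against Week 52, while eight weeks of tofacitinib or prednisone ending before Week 12 does not. No reason is given, and the list of modifications to the protocol's analysis does not mention the reset.

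**Working it through.** **1. Week 52 rules in SAP 9.3, side by side.**

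| Group | Week 52 window opens | Allowance up to Week 40 |
|---|---|---|
| Immunosuppressants | after Week 12 | up to 5 days |
| 5-ASA | after Week 12 | up to 5 days |
| Other small molecules | after Week 12 | up to 5 days |
| Systemic glucocorticoids, oral or rectal | after Week 12 | up to 7 days |
| Systemic glucocorticoids, parenteral | after Week 12 | one dose |
| Budesonide | after Week 12 | up to 5 days |
| Beclomethasone | after Week 12 | up to 5 days |
| Biologics | first dose | none |
| Procedures | first dose | none |

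All seven non-biologic drug groups reset at Week 12; biologics and procedures do not.

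**2. One case traced.** A participant takes oral prednisone above baseline dose for worsening symptoms from Week 3 to Week 10, remains on blinded drug and has no later rescue.
- Week 12 rule: more than 7 days above baseline by Week 8, so nonresponse at Week 12.
- Week 52 rule: nothing after Week 12, so no rescue event.
- Discontinuation event: none. Protocol 5.1 says noncompliance may, not must, end treatment, and protocol 3.1.1 keeps participants judged stable or improving at Week 12 on blinded drug.
- Protocol 10.4: nonresponder from Week 3 on, hence at Week 52.

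Had the course run to Week 14, the 14 days after Week 12 would exceed the 7-day allowance and the Week 52 rule would catch it. The gap is therefore rescue that ended, or returned to baseline dose, by Week 12 or within the allowance after it.

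**3. Endpoints exposed** (numbering of SAP 5.1): clinical remission (1), endoscopic improvement (2), 12-week corticosteroid-free remission (3), histologic-endoscopic mucosal improvement (7) and complete symptomatic remission (8), all at Week 52. Item 3 does not close the gap, because its steroid look-back reaches only to Week 52 − 12 = Week 40. Sustained remission (6) is protected by its Week 12 component. Items 4, 5 and 9 are Week 12 endpoints.

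**4. Scale.** Planning inputs from protocol 10.2: 122 and 61 participants, 34% and 14%, two-sided 0.05. Exact enumeration of Fisher's test gives 83.8% power, consistent with the stated 80% or more. The unpooled normal approximation gives 89.95%, in line with the stated 90%.

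The documents give no early-rescue rates. ASSUMPTIONS: a share *s* of placebo, and *s*/2 of etrasimod, has only early, transient rescue and stays on drug; a fraction *q* of these meets remission at Week 52; the planning rates hold under the protocol's rule. The SAP rule then adds *s·q* to placebo and *(s/2)·q* to etrasimod.

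| *s* | *q* | Placebo | Etrasimod | Difference | Participants, each arm | Fisher power |
|---|---|---|---|---|---|---|
| 5% | 10% | 14.5% | 34.25% | 19.75 | 0.3 | 82.4% |
| 10% | 20% | 16.0% | 35.0% | 19.0 | 1.2 | 78.1% |
| 15% | 30% | 18.5% | 36.25% | 17.75 | 2.7 | 70.2% |

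Top row: 61 × 0.05 × 0.10 = 0.3 and 122 × 0.025 × 0.10 = 0.3. Bottom row: 61 × 0.15 × 0.30 = 2.7 and 122 × 0.075 × 0.30 = 2.7.

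**5. Direction.** Let *e* be the share of an arm reclassified as remitters. If *e* is 3–5% on placebo only, the difference falls to 17–15 points (power 67.9–55.5%). On etrasimod only, it rises to 23–25 points (92.1–95.5%). With 14% in both arms under the protocol's rule, *e* of 3–5% on etrasimod only moves Fisher rejection from 3.6% to 6.0–10.6%. With 1–5% in both arms the difference stays at 20 points and power is 82.9–79.4%. The sign depends on which arm has more early rescue.

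**The case against.** The best defence is that the reset is a reasonable estimand choice. Rescue that stopped by Week 12 ended about 52 − 12 = 40 weeks before the assessment. The protocol's own pre-study washouts are shorter: 2 weeks for azathioprine and 6-mercaptopurine, 8 for methotrexate, 16 for ciclosporin and tacrolimus. SAP 9.3 says the effect of rescue depends on timing. Protocol 10.4 offers a per-protocol alternative and defers detail to the SAP, and Table 2 announces the move to estimands.

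Part of this stands. A timing-specific composite can be defended, and a reader might infer too readily that any remission in such a participant was induced by the other drug; after some 40 weeks the documents do not show that. But the SAP states no washout rationale. Its only example of timing is that rescue between Weeks 12 and 52 does not affect Week 12. The per-protocol set was removed, and Table 2 does not name this rule. Reading the applicable timepoints as all later ones would rescue the text, but the rule tables in 9.3 say otherwise, so at best the primary rule is ambiguous.

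Two stronger readings are tempting. One is that anyone rescued in the first 12 weeks can be a Week 52 remitter. That is too broad: continuing rescue is caught, discontinuation for any reason is already nonresponse, and all remission components must still be met. The other is that placebo is rescued more often and its rate therefore inflated. The documents give no rates by arm; if it were so, the bias would run against etrasimod.

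**Conclusion.** The point holds in its narrow form. SAP 9.3 departs, without declaring it, from the protocol's rule on a component of the primary estimand, and it treats non-biologic drugs differently from biologics and procedures without a reason. The participants concerned had non-biologic rescue that ended, or returned to baseline dose, by about Week 12 or within the short allowances after it, stayed on blinded treatment, and had no later rescue above the thresholds.

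The likely number is small: about 0.3 to 2.7 participants per arm, and 0.25 to 2.25 points off the planned 20-point difference, if early rescue is 5–15% on placebo and half that on etrasimod with 10–30% of these remitting. The upper end is generous, since 30% is more than twice the planned placebo rate. These are assumptions, not findings, and neither size nor direction can be settled from the documents. The powers use Fisher's test, on which the trial was sized, rather than the planned stratified Mantel–Haenszel analysis. The correction is worth making because the rule decides the primary endpoint and is cheap to settle while blinded.

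**What to change.** Before unblinding, in each of the seven non-biologic drug groups of SAP 9.3, open the first Week 52 window at first dose instead of after Week 12, still closing it at Week 40. Keep the existing Week 52 thresholds: more than 5 days, more than 7 days for oral or rectal systemic glucocorticoids, more than one parenteral dose. Report the present post-Week-12 rule as a sensitivity analysis for the primary endpoint and the key secondary endpoints assessed at Week 52.

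Do not simply declare that anyone meeting the Week 12 rule also fails Week 52. The Week 12 rules are strict near their own assessment. One extra day of 5-ASA at Week 9, or one intravenous steroid dose at Week 3, would become a Week 52 failure, while the same exposure at Week 30 would not.

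If the sponsor keeps the present rule, list it in Table 2 as a departure from protocol 10.4, give the reason, and run the from-first-dose version as the sensitivity analysis. In either case, say in SAP 2.2.3 and 5.3.1.1 which timepoints are applicable.

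The cost is one edited line per drug group and one extra run, with no new data; the rescue list is already to be finalized blinded. A few participants with early transient rescue become nonresponders. Keeping the thresholds aligns the timing with the protocol but still forgives short exposures, which the protocol text does not; Table 2 should say so.

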9.4. Programming Conventions for Outputs

OUTPUT CONVENTIONS

Outputs will be presented as shown in the Output shells.

DECIMALS, PERCENTAGES, AND P-VALUES

- If the original data has N decimal places, then the summary statistics should have the following decimal places:
 - Minimum and maximum: N
 - Mean (and LS Means), median: N + 1
 - SD or SE: N + 2

- Percentages will be reported to one decimal place. Where counts are zero, percentages will not appear in the output.
- P-values will be reported to three decimal places, except values < 1.000 but > 0.999 will be presented as > 0.999' (eg, 0.9998 is presented as <math>> 0.999).
- Values < 0.001 will be presented as '< 0.001' (eg, 0.0009 is presented as < 0.001). Rounding will be applied after the < 0.001 and > 0.999 rule

CONVENTIONS RELATED TO PHARMACOKINETIC DATA

All etrasimod concentrations will be reported and analyzed with the same precision as the source data provided by the bioanalytical laboratory regardless of how many significant figures or decimals the data carry. The derived PK data (etrasimod concentration) will be rounded to carry 3 significant digits and considered the source data for the calculation of descriptive statistics and the statistical analysis source data.

For the reporting of descriptive statistics, the mean, geometric mean, median, SD, % CV, and % geometric CV will be presented with 4 significant digits. The minimum and maximum will be presented with 3 significant digits.

DATES AND TIMES

Depending on data available, dates and times will take the form DDMMMYYYY or DDMMMYYYY:hh:mm.

SPELLING FORMAT

English US.

PRESENTATION OF TREATMENT GROUPS

For outputs, treatment groups will be represented as follows and in that order:

Table 13. Treatment Group Display

Treatment Group	For Tables, Figure, and Listings
Etrasimod	Etrasimod
Placebo	Placebo
Screen Failure	Screen Failure
Not Treated ^a	Not Treated

a. To be used for participants in safety listings who are randomized but do not receive study treatment.

PRESENTATION OF VISITS AND STUDY PERIOD

For outputs, visits and study periods will be represented as follows and in that order

Table 14. Visit and Study Period Display

Visit Name	Study Period
Screening	Screening
Baseline, Day 1, Week 2, Week 4, Week 8, Week 12, Week 16, Week 20, Week 24, Week 32, Week 40, Week 48, and Week 52	Treatment
End of Study/Early Termination Dependent on	Dependent on Analysis Visit assigned, described in Section 9.1.4
2-Week Follow-Up, 4-Week Follow-Up	Follow-Up

LISTINGS

All listings will be ordered by the following, unless otherwise specified:

- Randomized treatment group (or treatment received if it is a safety output), first by Etrasimod, then Placebo, then Screen Failure and then No Treatment (only in safety listings if there are any randomized participants who did not receive study treatment)
- Participant number (which is expected to incorporate study site/center)
- Date (where applicable)

9.5. Abbreviations

Table 15. List of Abbreviations

Abbreviation	Term
5-ASA	5-aminosalicylic acid
AE	adverse event
AESI	adverse events of special interest
ALC	absolute lymphocyte count
ALP	alkaline phosphatase
ALT	alanine aminotransferase
AST	aspartate aminotransferase
ATC	Anatomical Therapeutic Chemical
AV	atrioventricular
β-hCG	beta-human chorionic gonadotropin
BLQ	below the limit of quantitation
BMI	body mass index
Bpm	bpm beats per minute
CI	confidence interval
CM	concomitant medication

Table 15. List of Abbreviations

Abbreviation	Term	
CMH	Cochran-Mantel-Haenszel	
COVID-19	coronavirus disease 2019	
CR	copy reference	
CRP	C-reactive protein	
CS	clinically significant	
CSR	clinical study report	
CTCAE	Common Terminology Criteria for Adverse Events	
Ctrough,ss	average steady-state trough plasma concentration	
CV	coefficient of variation	
DBP	diastolic blood pressure	
DLCO	diffusing capacity of the lungs for carbon monoxide	
EAIR	exposure-adjusted incidence rate	
ECG	Electrocardiogram	
eCRF	electronic case report form	
eDISH	evaluation of drug-induced serious hepatotoxicity	
EIM	extraintestinal manifestation	
ES	endoscopic score	
FAS	Full Analysis Set	
FCP	fecal calprotectin	
FCS	fully conditional specification	
FDA	Food and Drug Administration	
FEF	forced expiratory flow	
FEV1	forced expiratory volume in 1 second	
FVC	forced vital capacity	
GGT	gamma-glutamyl transferase	
HR heart rate	heart rate	
HRQoL	health-related quality of life	
hs-CRP	high-sensitivity C-reactive protein	
IBDQ	Inflammatory Bowel Disease Questionnaire	
ICF	informed consent form	
JAK	Janus kinase	
LLQ	lower limit of quantitation	
LOESS	locally estimated scatterplot smoothing	
LS	least squares	
MAR	missing at random	
MCMC	Markov Chain Monte Carlo	
MedDRA	Medical Dictionary for Regulatory Activities	
mFAS	modified Full Analysis Set	
MMS	modified Mayo score	
MNAR	missing not at random	
NCS	not clinically significant	
NHI	Nancy Histological Index	
NRI	nonresponder imputation	
NRS	numeric rating scale	

Table 15. List of Abbreviations

Abbreviation	Term
OCT	optical coherence tomography
OLE	open-label extension
PFT	pulmonary function test
PAS	Primary Analysis Set
PGA	Physician's Global Assessment
PK	pharmacokinetics
PRES	posterior reversible encephalopathy syndrome
PT	preferred term
RB	rectal bleeding
RHI	Robarts Histopathology Index
RNA	ribonucleic acid
SAE	serious adverse event
SAP	statistical analysis plan
SBP	systolic blood pressure
SD	standard deviation
SDTM	Study Data Tabulation Model
SE	standard error
SF	stool frequency
SF-36	Study 36-Item Short Form Health Survey
SI	International System of Units
SOC	system organ class
SS	steady state
TB	tuberculosis
TEAE	treatment-emergent adverse event
TLC	total lung capacity
TME	targeted medical event
TMS	total Mayo score
TNFα	tumor necrosis factor alpha
UC	ulcerative colitis
ULN	upper limit of normal
ULQ	upper limit of quantitation
USPI	United States Prescribing Information
WHO	World Health Organization
WPAI-UC	Work Productivity and Activity Impairment Questionnaire – Ulcerative Colitis
